7 DATA MANAGEMENT

7.1 Data Storage and Management

Designated study site staff will record data required by the protocol into the CRFs and enter it into the electronic database. Authorized research staff will review the CRFs for completeness and accuracy and make any necessary corrections to the data entered into the electronic database. Information about study subjects will be kept confidential and managed according to the requirements of the Health Insurance Portability and Accountability Act of 1996 (HIPAA). Each subject screened and enrolled will be assigned a subject identification number (ID) and a list of subjects with their corresponding subject ID will be maintained separately from collected data. Physical CRFs will be stored in the research site in a locked office and electronic subject data will be locked in a password protected file on a secure internet server, accessed only by authorized research staff.

7.2 Records Retention

The Investigator will maintain the records of drug disposition, final CRFs (CDROM copies), worksheets, source documents, and all other study-specific documentation in accordance with ICH Guidelines. Essential documents should be retained until at least two (2) years after the investigation is formally discontinued.

7.3 Confidentiality

Subject information will be kept confidential as according to HIPAA requirements. Subject data will be stored and managed as outlined in section 5.3. All data records will be stored on site until 2 years after the investigation is formally discontinued. Paper records will be shredded and recycled. Records stored on a computer hard drive will be erased using a commercial software application designed to remove all data from the storage device.

8 DATA SAFETY MONITORING PLAN

8.1 Oversight

- 8.1.1 The principal investigator holds ultimate responsibility for the oversight and execution of the data and safety monitoring plan. This research site will be fully committed in the ongoing review and refinement of the trial's processes to assure subject safety, data validity and integrity, and regulatory compliance.
- 8.1.2 The principal investigator and medical monitor will monitor the safety data, assure protocol compliance, and conduct safety reviews to protect each subject's safety and welfare in this clinical investigation. The review process will be initiated after enrolling the first 10 subjects and every 10 subjects thereafter. The principal investigator will evaluate whether the study should continue unchanged, require modification, or closed to enrollment. [name] will serve as medical monitor and review all study related adverse events.
- 8.1.3 Case report forms (CRF) will be completed to capture protocol data. Two study coordinators will do separate CRF audits to assure data is accurate and complete and to assure adherence to study protocol. This will allow for identification of protocol deviations and areas in which practice can be improved. Audits will be done on all paper CRFs, which include the subject's informed consent form, ICF notes, subject eligibility, medical records, concomitant medication list, laboratory results, study procedures, visit notes, investigator notes, adverse event forms, subject drug diary, study drug accountability, and visit schedule. Proper filing of required regulatory documentation and subject CRFs, correct transcription of data, which will include checking for appropriate units of measure and legibility, will be monitored.

8.2 Criteria for protocol review

Safety related criteria will be in place for continued dosing of subjects. If any of the criteria, listed below, are met, all available data will be reviewed by the principal investigator to provide a recommendation regarding subsequent enrollment.

- A serious adverse event (SAE), deemed related to study treatment, occurs.
- Any subject on treatment experiences bleeding (major or spontaneous).
- Any subject on treatment experiences a Common Terminology Criteria for Adverse Events (CTCAE; v4.03) Grade 3 (or higher) event, deemed related to study treatment.
- Any other event that occurs in a subject on active treatment that is deemed to pose an unacceptable risk to other subjects in the study.

8.3 Subject Safety

8.3.1 Informed Consent

The informed consent form provides important safety information so each subject can make an informed decision on whether to participate in the trial. Subjects will be encouraged to complete the trial, but can withdraw at any time. By giving consent, health information, safety laboratory tests, vital signs measurements, and medical records will be collected and reviewed.

8.3.2 Physical Exam

A physical exam will be conducted by the investigators during the screening period after obtaining consent to evaluate the general status of the subject and to further elucidate patient symptoms, risk factors, or concerns that may increase the subject's risk for adverse reactions to the study treatment. Physical examinations will also be conducted by the investigators 30 ± 7 days post the first study drug dose.

8.3.3 Adverse Events Collection

Identification of adverse events is important in monitoring for patient safety. Adverse events will be collected during each study visit using a combination of modalities which include, spontaneous reporting of AEs by the patient in response to an open question from study personnel, observation, physical examination, or other diagnostic procedures performed during the study. All subjects will be instructed to report any new or worsening signs and symptoms or clinical events. Adverse events will be reported and assessed for clinical significance by the investigator. Unscheduled clinic visits, additional safety laboratory tests, and other diagnostic procedures may be necessary as recommended by the investigator to evaluate subject safety and to further investigate AEs reported by subjects in-between scheduled clinic visits.

8.3.4 Clinic Visits

Clinic visits will be scheduled as follows: 24 hours (+/- 2 hours) post initial dose of study drug, 30 ± 7 days post initial dose of study drug, 44 days post initial dose of study drug, and end of study visit. Clinic visits will allow for subject safety observations through patient assessment, review of subject's continued eligibility, safety laboratory test collection (for visit 4), vital signs measurement, physical examination (by investigators for visit 4), and recording of changes in concomitant medications and AEs.

8.3.5 Patient Counseling

All subjects will be counseled and given instructions in regards to study treatments. Subject education will include study treatment action, side effects, benefits and risks, dosage and administration, food-drug/drug-drug interactions, pregnancy/lactation warning, and when to call investigator/physician. Subjects will be instructed to inform physicians and dentists of study treatment intake and to list all prescription medications, over-the-counter medications, or dietary supplements they are taking or plan to take so study personnel knows about other treatments that may affect adverse event risk.

8.4 Study Treatment Discontinuation

Study treatment will be stopped and subject removed from study participation if any of the following criteria listed below are met:

- Withdrawal of informed consent
- Meeting an exclusion criteria post screening
- Any serious adverse event (as defined in section 8.8.2)
- Major or spontaneous bleeding
- Adverse events as defined by CTCAE v4.03, grade 3 or higher
- Allergic reaction to study treatment

- Pregnancy
- Subject requires an invasive or surgical procedure within the study period
- Non-compliance
- Subject develops a need for anticoagulant therapy
- Subject develops a need for antiplatelet therapy not originally assigned in his/her respective group
- Subject develops a need for any medication in the exclusion list
- Any other reason that the investigator feels would pose a significant hazard to the subject if investigational therapy were continued

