8.5 Subject Withdrawal

Subjects should also be withdrawn at any time if the investigator concludes that it would be in the subject's best interest for any reason.

Subjects may be considered withdrawn if they fail to return for visits, or become lost to follow up for any other reason. For subjects who are lost to follow-up (i.e., those subjects whose status is unclear because they fail to appear for study visits without stating an intention to withdraw), the investigator should show "due diligence" by documenting in the source documents steps taken to contact the subject (e.g. dates of telephone calls, registered letters). Subjects who are prematurely withdrawn from the study will not be replaced.

8.5.1 Subject Withdrawal Documentation.

If premature withdrawal occurs for any reason, the investigator should attempt to determine the primary reason for the withdrawal. The date and primary reason for premature withdrawal will be recorded on the Study Summary CRF. If applicable, the Investigator must provide appropriate follow-up medical care for all subjects who are prematurely withdrawn from the study, or must refer them for appropriate ongoing care.

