8.8.4 Procedures for Recording and Reporting of Adverse Events

8.8.4.1 All AEs will be reported to the principal investigator and medical monitor for evaluation. For both serious and non-serious AEs, the investigator has the primary responsibility for AE identification, documentation, grading, and assignment of attribution to the study treatment/intervention. The sponsor will consider the investigator's view when assessing the safety of the drug and determining whether to report expeditiously to the FDA and other regulatory agencies.

8.8.4.2 AEs occurring from the start of study medication administration through the last day of study participation must be recorded on the AE CRF with the following information:

- The intensity grade (grade 1, 2, 3, 4, 5; see CTCAE v4.03 grading)
- The relationship to the study drug(s)

- Attribution: An assessment of the relationship between the AE and the medical intervention (i.e., study drug administration). After naming and grading the event, the clinical investigator must assign an attribution to the AE using the following attribution categories:

RELATIONSHIP	ATTRIBUTION	DESCRIPTION
Unrelated to study treatment/intervention	Unrelated	The AE is clearly NOT related to the study treatment/intervention
	Unlikely	The AE Is doubtfully related to the study treatment/intervention
Related to study treatment/intervention	Possible	The AE may be related to the study treatment/intervention
	Probable	The AE is likely related to the study treatment/intervention
	Definite	The AE is clearly related to the study treatment/intervention

- The duration (start and end dates or if continuing at final exam)
- Occurrence (known risks for study drug/s, underlying illness or population)
 - Expected
 - Unexpected
- Other contributing causes
- Action taken with study drug
- Any other actions in response to event
- Outcome
 - Death related to AE
 - Recovered/resolved with sequelae
 - Not recovered/resolved
 - Recovered/resolved without sequelae
 - Recovering/resolving
 - Intervention for AE continues
 - Unknown
- Whether it constitutes a serious adverse event (SAE)

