8.8.6 Adverse Event Treatment

All AEs should be treated appropriately and managed as according to standard of care, at the discretion of the investigator. The action taken to treat the AE should be recorded on the AE CRF. A detected AE should be followed until its resolution or until the subject completes the study. Assessment should be made at each visit (or more frequently, if necessary) of any changes in severity, relationship to the study drug, the interventions required to treat it, and the outcome.

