8.8.6.1 Treatment for Bleeding Events

Bleeding will be documented using the Bleeding Academic Research Consortium (BARC) standard definition (Appendix A) (Mehran et al., 2011). Bleeding events should be treated according to standard clinical practice, depending upon the location and severity of the bleed. Withholding vorapaxar for a brief period will not be useful in managing an acute bleeding event because of its long half-life. There is no known treatment to reverse the antiplatelet effect of vorapaxar.

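### Removing subjects from the study when treatment stops ends their offset PD and non-serious AE data, and leaves completer analyses that can be biased

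*Combined protocol and SAP*

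**What the plan says.** Section 8.4 gives one event two consequences: "Study treatment will be stopped and subject removed from study participation if any of the following criteria listed below are met". The list covers every SAE, "Major or spontaneous bleeding" and "Adverse events as defined by CTCAE v4.03, grade 3 or higher", with no causality condition. Section 8.5 adds: "Subjects who are prematurely withdrawn from the study will not be replaced".

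Most data collection depends on participation. Section 8.8.4 says "AEs occurring from the start of study medication administration through the last day of study participation must be recorded on the AE CRF", and Section 8.8.6 says "A detected AE should be followed until its resolution or until the subject completes the study". Section 8.8.8 treats SAEs differently. They are reported up to 28 days after the subject leaves, and recurrence, complications or progression of a known SAE are reported without a time limit.

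On persistence, Section 8.8.6.1 states "Withholding vorapaxar for a brief period will not be useful in managing an acute bleeding event because of its long half-life". Offset is an aim in Section 1.1 and a secondary endpoint in Section 5.2.2. It is measured two and four weeks after vorapaxar ends (Section 9, Visits 5 and 6).

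The primary endpoint (Section 5.2.1) needs a value after 3-4 weeks of vorapaxar. Section 6 analyses change scores with a paired t-test or Wilcoxon signed ranks test. The plan gives no analysis set, no missing-data rule, no early-termination visit and no PD sample at stopping.

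**The concern.** A subject who tolerates vorapaxar is followed for two further visits after the last dose, with PD and AE collection at both. A subject who stops because of a bleed is given neither. Follow-up is thus shortest for the subjects most informative about safety, in a study that describes itself as a pharmacodynamics and safety investigation.

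There is also a selection question. A subject removed before Visit 4 has no primary value, and one removed at any time before Visit 5 has no offset value. Bleeding is plausibly related to the antiplatelet effect being measured. If it is, the remaining subjects are a selected set. Should removed subjects respond more strongly, completers would understate the drug effect. Groups take one, two or three agents (Section 3.1.2), so the between-group comparisons could also be affected.

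**Working it through.** **1. Plan's own figure.** Section 5.1 assumes that 25 per group is sufficient. It gives no effect size, SD, power or dropout, so the figure cannot be reproduced. The detectable effects below are illustrations that add 80% power and a two-sided test to the stated 0.05 level.

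**2. Follow-up lost after stopping.** Visits 5 and 6 are two intervals of 14 ± 3 days, so a completer has 14 + 14 = 28 (± 6) days of AE recording and two PD samples after Visit 4. A subject removed on stopping has 0 days of non-serious AE recording and 0 samples. The SAE window of 28 days is about the same length as the planned offset period.

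Counted from the first dose, nominal follow-up is 30 + 14 + 14 = 58 days with five post-dose PD samples (2 h, 24 h, Visits 4, 5 and 6). Removal on day D loses 58 − D days of AE recording: 57 if just after Visit 3 (D = 1), 28 if at the nominal Visit 4 (D = 30). Removal between Visits 3 and 4 loses 3 of the 5 samples.

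**3. Size of completer bias.** Let d be the share removed and k the difference in mean change, removed minus retained, in SD of the change score. With retained mean m, the mean of all dosed subjects is (1 − d)m + d(m + k) = m + dk, so completers are off by dk. The documents give neither d nor k; both are assumed. The detectable change δ solves P(T > t(0.975, n−1)) = 0.80, where T is noncentral t with n − 1 degrees of freedom and noncentrality δ√n.

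| Removed of 25 | n left | Bias, k = 0.5 | Bias, k = 1.0 | Detectable change (SD) | Bias ÷ detectable |
|---|---|---|---|---|---|
| 0 | 25 | 0 | 0 | 0.58 | 0 |
| 1 (4%) | 24 | 0.02 | 0.04 | 0.60 | 3-7% |
| 2 (8%) | 23 | 0.04 | 0.08 | 0.61 | 7-13% |
| 3 (12%) | 22 | 0.06 | 0.12 | 0.63 | 10-19% |
| 5 (20%) | 20 | 0.10 | 0.20 | 0.66 | 15-30% |

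If k = 0 the bias is zero at every d.

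**4. Second model.** Suppose the top share d of a variable correlated ρ with PD change is removed. The bias is then ρφ(z(1−d))/(1 − d). For ρ = 0.3 to 0.6 it is 0.03-0.05 SD at 4% and 0.11-0.21 SD at 20%. The ceiling ρ = 1, where response alone decides removal, gives 0.09 and 0.35 SD.

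**5. Precision and group differences.** For a true change of 0.58 SD, power falls from 80% at n = 25 to about 76% at n = 23 and 70% at n = 20. A between-group contrast is distorted by the difference of the two dk terms. Equal terms cancel; with k = 1.0 in both groups, 20% against 4% removed gives 0.20 − 0.04 = 0.16 SD.

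**6. Sections that do not agree.**
- Section 3.3 stops drug permanently with a CRF entry and does not mention removal; Section 8.4 requires removal.
- Section 8.8.8 asks whether a subject continued or withdrew after an SAE; Section 8.4 leaves no option to continue.
- Section 8.8.7 says non-serious AEs that do not lead to stopping drug are not collected; Sections 8.8.4 and 8.8.5 collect AEs generally.

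**The case against.** A reader might infer that removal ends all AE follow-up. It does not: Section 8.8.8 covers SAEs, and Section 8.5 requires medical care or referral where applicable. Section 8.8.6 can even be read as following the triggering bleed to resolution, since a removed subject never completes the study. What removal closes is the window for new non-serious events. If Section 8.8.7 governs, few of those would have been collected anyway. That objection stands as a limit on the loss. It also shows a contradiction to resolve, because Section 8.8.3 separately calls for bleeding to be documented by BARC type.

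A reader might also infer that the results are biased, and more so in Group 4. The documents give no removal rate and no link between bleeding and PD change. Several triggers, such as non-compliance, surgery or an SAE of any cause, need not track response. So the bias is possible, not shown, and unequal removal across groups is a conjecture. Nor is a half-life or offset duration given, so persistence cannot be quantified.

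Finally, it is tempting to make all dosed subjects with any post-dose sample the primary set. That would put 2-hour, 24-hour or off-drug values into an endpoint defined at 3-4 weeks of vorapaxar. Later samples may also reflect other changes: Section 3.1 counts aspirin and clopidogrel as study drugs, so stopping may involve them, whereas the planned offset period keeps them going (Section 9.2.5). This objection stands.

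Sections 2.2 and 2.4 might be read as allowing enrolment to continue until 25 per group have usable data. That sits uneasily with the bar on replacement, and topping up would restore precision without undoing selection.

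**Conclusion.** The concern holds in a limited form. On the wording alone, a subject removed for bleeding, an SAE or a grade 3+ AE before the offset visits contributes no further offset PD data, and new non-serious AEs and bleeding go unrecorded after removal. SAE reporting is preserved.

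The maintenance and offset analyses are completer analyses by default. Any bias is 0.02-0.20 SD under assumed removal of 4-20% and an assumed 0.5-1.0 SD difference. That is about 3-30% of the within-group change detectable with the subjects left. It is zero if removal is unrelated to response. The data loss is certain whenever a subject is removed; the bias is a reasonable inference of unknown size. The change should be made, because samples and events not collected cannot be recovered later.

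**What to change.** Leave the treatment-stopping criteria unchanged and separate them from study withdrawal.

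- **Follow-up.** Unless consent is withdrawn, keep the subject in the remaining scheduled visits, timed from the last vorapaxar dose. Record all AEs and bleeding to the end-of-study visit. Collect PD at those visits where feasible, with a sample at stopping if the subject is seen.
- **Analysis.** Keep the 3-4 week on-treatment comparison as primary. Report removals by group and reason. Flag post-stopping PD values, including any change in background or new antithrombotic drugs, and use them only in offset summaries and a sensitivity analysis.
- **Consistency.** Reconcile Sections 3.3, 8.4, 8.8.4, 8.8.6, 8.8.7 and 8.8.8 on whether stopping drug means removal, and on which AEs are collected and for how long.

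The cost is a protocol amendment and a few extra visits and draws (about 25-30 ml each, Section 4.8), in subjects who may have stopped for bleeding and who have no direct benefit (Section 8.7). Some PD values will be confounded by other drug changes. The fix recovers offset and safety data; it does not supply the missing 3-4 week on-drug value.

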8.5 Subject Withdrawal

Subjects should also be withdrawn at any time if the investigator concludes that it would be in the subject's best interest for any reason.

Subjects may be considered withdrawn if they fail to return for visits, or become lost to follow up for any other reason. For subjects who are lost to follow-up (i.e., those subjects whose status is unclear because they fail to appear for study visits without stating an intention to withdraw), the investigator should show "due diligence" by documenting in the source documents steps taken to contact the subject (e.g. dates of telephone calls, registered letters). Subjects who are prematurely withdrawn from the study will not be replaced.

8.5.1 Subject Withdrawal Documentation.

If premature withdrawal occurs for any reason, the investigator should attempt to determine the primary reason for the withdrawal. The date and primary reason for premature withdrawal will be recorded on the Study Summary CRF. If applicable, the Investigator must provide appropriate follow-up medical care for all subjects who are prematurely withdrawn from the study, or must refer them for appropriate ongoing care.

8.6 Human Subjects Protection (Risks, Benefits, and Alternatives)

8.6.1 Risks

8.6.1.1 Potential Loss of Privacy

Protected health information (PHI) will be collected during the study. The risk for breach of confidentiality and privacy will be minimized by shielding the subjects unlinking his or her identity from his or her personal health information.

8.6.1.2 Potential Adverse Events

The subject's medical history, significant laboratory and diagnostic tests, and concomitant medications will be thoroughly reviewed prior to enrollment to reduce incidence of adverse events.

8.6.1.3 Study Drug

8.6.1.3.1 Bleeding

GUSTO severe bleeding was defined as fatal, intracranial, or bleeding with hemodynamic compromise requiring intervention; GUSTO moderate bleeding was defined as bleeding

requiring transfusion of whole blood or packed red blood cells without hemodynamic compromise. (GUSTO: Global Utilization of Streptokinase and Tissue Plasminogen Activator for Occluded Arteries.). Vorapaxar increased GUSTO moderate or severe bleeding by 55%. It increases the risk of bleeding, including intracranial hemorrhage (ICH) and fatal bleeding. Note that the risk of bleeding with vorapaxar increases in proportion to the subject's underlying bleeding risk. Provide treatment if subject shows signs and symptoms of bleeding.

Thienopyridines, including clopidogrel, increase the risk of minor and major bleeding. In the CURE trial, Plavix use with ASA was associated with an increase in major bleeding (primarily gastrointestinal and at puncture sites) compared to placebo with ASA. Gastrointestinal hemorrhage occurred at a rate of 2% in those taking clopidogrel vs. 2.7% in those taking ASA in the CAPRIE trial. Other bleeding events that were reported more frequently in the clopidogrel group were epistaxis and hematoma.

